 - c) greater improvement or lesser impairment of quality of life after reconstruction of floor of lesser pelvis
2. To study if the different rehabilitation programmes used reflect differences in outcome measures in subgroup analyzes for both methods of reconstruction
3. To compare the health economic costs with the two techniques and to perform a cost-utility analysis (QALYs gained). The health economic analysis is optional to participating centres. Costs and health economics will be calculated only in centres that have routine registration (in electronic databases) of operation time, time at ICU, days in hospital, connected reoperations, connected readmissions and outpatient visits related to the index operation.

Investigational plan

Endpoints of study

1. Primary endpoint: Performance in Timed-stands test (TST)[9, 10]reflecting physical performance at 6 months from operation.
2. Secondary endpoints:
 1. Change in physical performance (3 months, 6 months and 1 year compared to preoperative)
 2. Primary wound healing assessed with the Southampton Wound Assessment Scale (SWAS)[11] at 3 months from operation
 3. Complications according to classification by Dindo-Clavien[12] (3 months, 6 months and 1 year)
 4. Proportion of persistent perineal sinus or fistula (3 months, 6 months, 1 year)
 5. Ability to sit (3 months, 6 months, 1 year)
 6. Change of pain and discomfort in gluteal region measured with VAS (3 months, 6 months and 1 year compared to preoperative)
 7. Change of quality of life measured with EQ-5D and EORTC forms C30 and CR29 (3 months, 6 months and 1 year compared to preoperative)
 8. Quality of life spot measures at 3 months, 6 months and 1 year

9. Length of hospital stay, costs of surgical treatments and QALYs gained at one year
10. Local recurrence during study period

Hypotheses of study

Primary hypothesis:

1. The reconstruction of lesser pelvis floor with APCI will result in better physical performance in operated patients compared to patients operated on with GMF.

Secondary hypotheses:

1. The assumed decrease of physical performance after the APCI operation will be less than after the GMF operation.
2. The reconstruction of lesser pelvis floor with APCI will result in better wound healing and less wound complications than the GMF operation.
3. The reconstruction of lesser pelvis floor with APCI will result in better ability to sit and lesser pain and discomfort in the gluteal region than the GMF operation,

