4. The reconstruction of lesser pelvis floor with APCI will result in better quality of life than the GMF operation.
5. The reconstruction of lesser pelvis floor with APCI will result in lower costs of treatment and more QALYs gained than the GMF operation.
6. The local recurrence rate is not related to the method of reconstruction of lesser pelvis

Noninferiority hypothesis:

1. The reconstruction of lesser pelvis floor with APCI will result in clinically equivalent physical performance provided that results will be within defined noninferiority margins, see below.

Noninferiority margin:

The noninferiority margin is set to 10%. Interpretation, see section Data analysis methods.

Summary of study design

The study is multi-centre, prospective randomised and with parallel assignment. Centres that treat locally advanced rectal cancers with the extended abdominoperineal excision of rectum (EAPE)[7] can participate provided that:

1. the operative technique is standardized according to this protocol, see section Surgical methods
2. the centre/unit has resources for examinations of participants by a physiotherapist or a nurse
3. the centre/unit has one investigator in charge of the study locally
4. the centre/unit has an operative volume that enables at least 6 patients to be included/randomised during the anticipated three year study phase for inclusions

Centres that do not operate the rectal cancers included in this study can participate by arranging the preoperative examination and physical tests as well as follow-up of patients that are referred to other centres for the operation. In these cases the operating centre cares for the randomisation, operation and start of postoperative rehabilitation while the study follow-up and final rehabilitation can be completed at the patients' primary referral

hospital. The primary referral hospital needs a site investigator in charge of study patients just like centres that do the operations.

Patients with primary or recurrent cancers of rectal origin can be included but individual patients can be included only once. Concomitant therapies are allowed and preoperative or postoperative radiation therapy and/or chemotherapy may be given or not according to local multidisciplinary team (MDT) decisions.

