The participants are examined by a physiotherapist or a study nurse who is familiar with the protocol. Examinations of physical performance, wound healing and registration of quality of life and background information takes place:

1. within one week before the start of radiotherapy (or operation if examination before RT can not be accomplished) (wound healing excluded)
2. three months after the operation
3. six months after the operation
4. one year after the operation
5. at one late time point 2-5 years after the operation if previous analyses indicates a need for long time follow-up. The long time follow-up is optional for participating centres and will be decided later.

A separate detailed protocol of standardized examination procedures will be available for the physiotherapists and nurses involved in the study. A pre-study meeting for standardization of examinations will be arranged for participating centres.

The standardisation of operations will be secured with site visits from (or to) Stockholm Karolinska Sjukhuset Solna where the standard for GMF and APCI operations is defined.

The enrolment of a patient in the study is finalized with the randomization procedure on Internet. The web application at www.norrlandskirurgi.se is used for randomization.

The randomization is computed in blocks and stratified by:

- Centre
- Mode of preoperative radiotherapy (RT)
 - Short preoperative RT, (5 x 5 GY), **operation within one week from last RT dose**
 - Short preoperative RT, (5 x 5 GY) or long preoperative RT (25 x 1,8/2 GY), **operation 4 - 8 weeks from last RT dose**
 - Earlier RT for organs in the lesser pelvis in connection to a previous therapy but no additional RT before the current operation or other RT dose or timing of operation

The stratification and block randomization ensures that all above defined subgroups of patients will contain patients allocated evenly (or close to evenly) to both study arms. The size of the randomisation blocks will vary within predefined limits and the size of the block under use will be chosen by random from the alternatives given of limits.

Flowchart of NEAPE study

Surgeon and study nurse

MDT conference

- Identify APE and EAPE candidate patients =eligible rectal cancer patients
- Study nurse enter identified patients in register at www.norrlandskirurgi.se

Study nurse

For EAPE candidates, send invitation for preoperative visit to surgeon and physiotherapist or study nurse

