Definitions of oncologic result

Local recurrence and/or metastatic disease are registered as soon as the attending surgeon has verified the existence of the complication. The diagnosis may be based on clinical examination, histology, radiological examination or a combination of investigations.

Information of local recurrence and metastatic disease will be registered in the postoperative follow-up form (see Appendix) at every follow-up visit.

Safety measures, early postoperative complications, and other clinical adverse events

Postoperative complications will be registered in the Swedish Colorectal Cancer Registry via a web application (INCA) directly by the participating units within Sweden. The register collects data of postoperative complications occurring in the time intervals 1-30 days and from 31 days until five years after the index operation. This registration is routine for all patients treated for rectal cancer in Sweden and is not changed for patients participating in the study. Interpretation of data of postoperative complications can be done for the early period as soon as the registration of the operation is completed in the register. The delay of registration of the operation in the Swedish Colorectal Cancer Registry may vary between different units but should be done within two months. It is the attending surgeon who completes the register. The registration in the Swedish Colorectal Cancer Registry of complications occurring in the later period (31 days until 5 years) takes place after every follow-up visit and this data can be used as a safety measure during the study.

Participating units outside Sweden can not register early or late postoperative complications in the Swedish Colorectal Cancer Registry (INCA) but a similar registration form will be available via the study homepage web application (www.norrlandskirurgi.se) for use of units outside Sweden.

Both the surgeon and the physiotherapists (and study nurses) involved in the follow-up examinations of patients should report every serious adverse event that is observed among enrolled patients later during the study. The reports of adverse events are made via the study homepage web application for units outside Sweden and in the Swedish Colorectal Cancer Registry (INCA) for units in Sweden. These reports are continuously collected and evaluated by the study administration, and if any safety concern with the study appears, an independent advisor is consulted.

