Once per year an independent advisor that together with the PI has the authority to stop the study if serious unexpected safety issues can be observed will evaluate the collected data of clinical adverse events. If the independent advisor and the PI make a decision to stop the study, the decision must be written and motivated in detail and distributed to all participating centres without delay.

Quality control and quality assurance

To ensure accurate and reliable data the study administration will do the following:

- Provide instructional material to the study sites, as appropriate (manual for physical examination etc.)
- Update study homepage at www.norrandskirurgi.se with relevant information and study material
- Start-up training, meeting with investigators
- Be available for consultation
- Conduct quality review of database (a monitor may be sent to participating centres)

Data analysis methods

Sample size

The sample size is calculated with the following assumptions:

- Estimated proportion of patients with low performance in TST with GMF 63%
- Estimated proportion of patients with low performance in TST with APCI 30%
- Estimated loss of data/cases 20% (mortality etc.)

The calculation gives that a total of 108 patients (54 patients in each study arm) are needed with 90% power and a significance level of 0.05 (alpha).

If the anticipated three-year inclusion phase of the study is too short for including 108 patients an alternative power calculation with 80% power will be used instead and the study will include a total of 80 patients only before the inclusion phase will be closed.

Interpretation of noninferiority

The noninferiority margin for the study is set on the basis of a minimally important clinical effect, which is a subjective judgement of the best expertise available. This approach remains the only alternative since there are no historical placebo controlled trials in the field for guidance and for practical reasons such trials are not possible to conduct.

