Preoperative oncologic treatment and pre- and postoperative tumour classification (cTNM and pTNM) will be registered in (and retrieved from) the Swedish Colorectal Cancer Registry for Swedish patients and for patients outside Sweden a similar form with TNM data is completed via the study homepage web application by the local investigator. The pTNM classification will also be included in the summary reports.

Primary analysis

Performance in Timed-stands test (TST) measured in seconds (time) will be compared between study arms at 6 months from the operation and tested with appropriate statistical tests. The proportion of patients that perform worse than the upper limit of reference values may be used as a parameter for comparison. TST reflects physical performance that is the primary outcome of the study.

Secondary analyses

1. The change of physical performance, i.e. the difference between preoperative and postoperative results in TST at 3, 6 and 12 months will be compared between study arms.
2. Primary wound healing at 3 months is categorized in subclasses (SWAS[11]) and the proportions of patients in different classes are compared between study arms.
3. Complications are categorized according to classification by Dindo-Clavien [12] and the proportions of patients in different classes are compared between study arms at 3, 6 and 12 months.

4. Ability to sit is defined in three classes and the proportions of patients in different classes are compared between study arms at 3, 6 and 12 months.
5. Pain and discomfort in gluteal region measured with VAS and analyzed with appropriate statistical methods. Comparisons will be done at 3, 6 and 12 months.
6. Quality of life is measured with EQ-5D and EORTC forms C30 and CR29 and the individual responses are calculated to a health utility index using an appropriate table/tariff for the general population[25, 26] Spot measures at 3, 6 and 12 months and differences between pre-treatment and postoperative measurements will be compared.
7. The proportion of patients that present local recurrence during the study period will be compared between study arms.

Subgroup analyses

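### Secondary hypothesis 6 asserts that local recurrence is unrelated to the reconstruction, but a non-significant comparison in a trial sized only for the timed-stands test cannot confirm it

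*Protocol*

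**What the plan says.** Under Hypotheses of study, the sixth secondary hypothesis is "The local recurrence rate is not related to the method of reconstruction of lesser pelvis". Secondary hypotheses 1 to 5 each state a direction in favour of the collagen implant (APCI); only the sixth states an absence of effect.

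The matching item under Endpoints of study is "Local recurrence during study period". Secondary analyses gives the method: "The proportion of patients that present local recurrence during the study period will be compared between study arms". The study period is given no end date or time point. In the flowchart, the attending surgeon's last scheduled follow-up visit is at 12 months.

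The Sample size section is built on TST alone: low performance in 63% with the gluteus flap (GMF) against 30% with APCI, and 20% loss. It concludes that "a total of 108 patients (54 patients in each study arm) are needed with 90% power". If recruitment is slow, a fallback of 80 patients in total at 80% power applies. The 10% noninferiority margin is tied to physical performance, the main outcome, and not to recurrence.

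**The concern.** For a directional hypothesis, a non-significant result means that the hypothesis was not supported. For hypothesis 6 the logic is reversed: a non-significant result looks like confirmation. That would be reasonable only if the trial were large enough for a real difference to show, or if the result were judged against a stated tolerance. A trial sized for a 33-point difference in TST performance (63% minus 30%) is unlikely to be large enough for an outcome that may affect a few patients per arm.

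At stake is what the trial may say about an oncological outcome. The Introduction gives local recurrence as the reason for the enlarged operation, so a statement that the reconstruction makes no difference to it would carry weight with readers.

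The open-ended study period adds a smaller difficulty. If it means the calendar life of the trial, a patient recruited at the start of the three-year inclusion phase could be observed for about 3 + 1 = 4 years and one recruited at the end for 1 year. The proportion would then refer to no single time point.

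**Working it through.** **Inputs from the protocol.** TST low performance 63% and 30%, alpha 0.05, power 90% or 80%, loss 20%, total 108 or 80 (Sample size). Local recurrence after abdominoperineal excision reported as 5% to 47%, with no time horizon (Introduction). Data from patients who die or are lost are usable up to discontinuation (Discontinuations).

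**Step 1: reproduce the planned sample size.** For two proportions with unpooled variance and two-sided alpha 0.05:

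n = (z₀.₉₇₅ + z_power)² × [p₁(1−p₁) + p₂(1−p₂)] / (p₁−p₂)²

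- 90% power: (1.960 + 1.282)² × (0.2331 + 0.2100) / 0.33² = 42.75, so 43 per arm; 43/0.8 = 53.75, so 54 per arm and 108 in total.
- 80% power: 31.94, so 32 per arm; 32/0.8 = 40 per arm and 80 in total.

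Both planned totals are reproduced, and recurrence plays no part in them. For recurrence the denominator is therefore about 43 per arm, 32 under the fallback after loss, and at most 54 if every randomised patient counts.

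**Step 2: power to detect a doubling of recurrence.** Exact power of the two-sided Fisher test is the sum, over all pairs (i, j) with Fisher p ≤ 0.05, of Bin(i; n, p₁) × Bin(j; n, p₂). The usual normal-approximation power is in brackets.

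| True rates | 32 per arm | 43 per arm | 54 per arm |
|---|---|---|---|
| 5% vs 10% | 2% (11%) | 5% (14%) | 7% (16%) |
| 10% vs 20% | 11% (20%) | 17% (25%) | 21% (31%) |
| 20% vs 40% | 33% (41%) | 45% (53%) | 55% (62%) |

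The rates are assumptions taken from within the protocol's 5% to 47% range. At 5% against 15%, a tripling, Fisher power with 43 per arm is 21%. By the normal approximation, 80% power with 43 per arm and 5% in one arm would need about 27% in the other.

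**Step 3: what a null result would leave open.** Take 2 recurrences among 43 in each arm, the number expected at 5% (43 × 0.05 = 2.15). The Wilson 95% limits for 2/43 = 4.65% are 1.29% and 15.46%. Newcombe's interval for the difference has half-width √[(4.65 − 1.29)² + (15.46 − 4.65)²] = √(3.36² + 10.81²) ≈ 11.3 points, so it runs from -11.3 to +11.3. The same calculation gives ±10.2 points for 3/54 in each arm and ±14.6 points for 2/32. None of these excludes a 10-point excess, such as 15% against 5%.

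At higher rates power rises but the interval widens. With 43 per arm it is about ±17 points at 20% and about ±20 points at 47%.

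**Step 4: what the hypothesis would need.** To detect a doubling with 80% power, two-sided 0.05, takes 435 per arm for 5% vs 10% and 199 for 10% vs 20%. To exclude a 10-point excess when true rates are equal (one-sided 0.025, 80% power) takes (1.960 + 0.842)² × 2 × 0.05 × 0.95 / 0.10² = 74.6, so 75 per arm at 5%; the same formula gives 142 at 10% and 252 at 20%. The 10-point margin is illustrative only, as the protocol sets none for recurrence.

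**The case against.** Several points on the other side are sound.

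- **No claim of equivalence is written down.** A reader might infer that a null result will be reported as oncological equivalence. The documents do not say so: the analysis is only a comparison, and the rule for reading non-significance under Interpretation of noninferiority concerns the main outcome. What stands is narrower: the hypothesis is worded so that a null result appears to confirm it.
- **Ascertainment is not confined to study visits.** A reader might infer this from the visit forms, but Definitions of oncologic result has recurrence recorded once the surgeon has verified it, in addition to the form at each visit.
- **Late data are not shown to depend on which centres opt in.** The protocol says of the examination at 2 to 5 years "The long time follow-up is optional for participating centres and will be decided later". That item belongs to the list of physiotherapist or nurse examinations, whereas recurrence is recorded by the surgeon. It does not follow that late recurrence data would come from self-selected centres.
- **Longer follow-up is a separate question.** The Swedish registry text says "The register collects data of postoperative complications occurring in the time intervals 1-30 days and from 31 days until five years after the index operation", which may suggest a required 3- or 5-year readout. That would add to the trial's scope, and the protocol does not state that units outside Sweden follow patients that long.
- **Choice of figures.** Fisher's test is conservative, 43 is the number evaluable for TST, and 5% is the low end of the quoted range. The table therefore also shows 54 per arm, the normal approximation and higher rates. Near 47% a doubling would be detected, but the interval would still be too wide to support no relation.
- **Analysis-plan content.** A margin or a confidence interval could be given in an analysis plan that is not shown, so their absence here is not a fault in itself. The wording of the hypothesis, the sample size and the visit schedule are fixed in the protocol.

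**Conclusion.** The point holds in limited form. Hypothesis 6 states an absence of effect, in a trial whose size was set for TST alone. For a true doubling from 5% or 10%, Fisher power is 5% and 17% with 43 per arm (2-7% and 11-21% across 32 to 54 per arm). A non-significant result would therefore be expected in at least 79% of trials even though recurrence had doubled (100 − 21 = 79, the most favourable of these cases). With 2 events per arm among 43, the data would be compatible with a difference of about 11 points in either direction. Such a result cannot confirm the hypothesis.

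This rests on assumed recurrence rates within the protocol's quoted range, which has no time horizon; rates at 12 months may be lower, and power would then be lower still. The weakness is minor: it concerns one secondary hypothesis and leaves the primary endpoint and its sample size untouched.

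**What to change.** Replace hypothesis 6 by a descriptive aim. Suggested wording: local recurrence within 12 months of operation will be reported by assigned arm for the intention-to-treat population, as the difference in proportions with its 95% confidence interval; no conclusion that recurrence is unrelated to the reconstruction will be drawn from a non-significant test. Use the same 12-month time point in the secondary endpoint and in the secondary analysis, in place of the undefined study period.

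The cost is a change of wording in three places. It needs no extra patients, visits or data, since the surgeon's visit at 12 months is already scheduled. The downside is that the trial gives up a claim of no relation, which its size could not support. A later readout from routine follow-up could be considered as an option where it is feasible, but this point does not depend on it.
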